#### 7.4. Assigning Severity Rating for Adverse Events

Severity describes the intensity of a specific event (as in mild, moderate, or severe myocardial infarction); the event itself, however, may be of relatively minor medical significance, such as a severe headache. This is not the same as "serious," which is based on patient/event outcome or action taken.

The investigator must determine the severity of each adverse event according to the National Cancer Institute CTCAE. For terms not specified with the CTCAE, the criteria in Table 7-1 should be used to determine the grade severity.

Table 7-1 Criteria for Determining the Grade/Severity of Adverse Event Terms Not Specified by the National Cancer Institute CTCAE

Grade	Criteria
1/Mild	Asymptomatic or mild symptoms, clinical or diagnostic observations only; intervention not indicated
2/Moderate	Minimal, local, or noninvasive intervention indicated; limiting age-appropriate instrumental activities of daily living
3/Severe or medically significant	Not immediately life-threatening; hospitalization or prolongation of hospitalization indicated; disabling; limiting self-care activities of daily living
4/Life-threatening	Life threatening consequences; urgent intervention indicated
5/Death	Death related to adverse event

Adverse event severity should be recorded in the appropriate section of the adverse event case report form and in the patient's source documents.

## 7.5. Adverse Events of Clinical Interest Reporting

Adverse events of clinical interest in this study are defined as any increase in ALT or AST  $\geq$  3 x ULN.

Any ALT or AST elevation of this degree or greater occurring during the Randomized Treatment Period or the Follow-Up visit should be reported to the sponsor using the Serious Adverse Event Form within 24 hours of the study site personnel's knowledge of the event (see Section 7.6), even if the event does not meet SAE criteria. Additional instructions for evaluating patients with an increase in ALT or AST  $\geq$  3 x ULN may be found in Appendix 7, even if the event does not meet SAE criteria.

# 7.5.1. Criteria for Temporary Withholding of Study Drug in Association with Liver Test Abnormalities

Hepatic enzymes will be monitored in accordance with FDA drug-induced liver injury guidelines [FDA, 2009].

If the following liver test abnormalities develop, study drug should be withheld immediately with appropriate clinical follow-up (including repeat laboratory tests, until a patient's laboratory profile has returned to normal/baseline status), and the event reported as a serious adverse event:

- ALT or AST  $> 8 \times ULN$ ; or
- ALT or AST > 5 x ULN and persists for more than 2 weeks; or
- ALT or AST > 3 x ULN and total bilirubin > 2 x ULN or the INR > 1.5; or
- ALT or AST > 3 x ULN with appearance of fatigue, nausea, vomiting, right upper quadrant pain or tenderness, fever, rash and/or eosinophilia (> 5%).

Rechallenge may be considered if an alternative cause for the abnormal liver tests (ALT, AST, total bilirubin) is discovered and the laboratory abnormalities resolve to normal or baseline values. The investigator and sponsor must discuss and agree with any decision to rechallenge.

Rechallenge should not occur when the etiology of the liver test abnormalities is considered possibly drug induced.

# 7.5.2. Criteria for Permanent Discontinuation of Study Drug in Association with Liver Test Abnormalities

Study drug treatment should be discontinued permanently if all of the following 4 criteria are met (ie, potential severe drug-induced liver injury/Hy's law case):

- 1. AST or ALT increases to  $\geq 3$  x ULN; AND
- 2. Total bilirubin increases to  $> 2 \times ULN$  or INR > 1.5; AND
- 3. Alkaline phosphatase value does not reach 2 x ULN; AND
- 4. No alternative cause explains the combination of the above laboratory abnormalities; important alternative causes include, but are not limited to the following:
  - Hepatobiliary tract disease;
  - Viral hepatitis (eg, hepatitis A/B/C/D/E, Epstein-Barr virus);
  - Exposure to hepatotoxic agents/drugs or hepatotoxins, including herbal and dietary supplements, plants, and mushrooms;
  - Alcoholic hepatitis;
  - Nonalcoholic steatohepatitis;
  - Autoimmune hepatitis.

If an alternative cause for hepatotoxicity is identified, then it should be determined (based on the severity of the hepatotoxicity or event) whether study drug treatment should be withheld or permanently discontinued as appropriate for the safety of the patient.

#### 7.6. Serious Adverse Event Reporting

Using a Safety Reporting Form, all serious adverse events must be reported within 24 hours of the study site personnel's knowledge of the event, regardless of the investigator assessment of the relationship of the event to study drug.

The contact information for submission of serious adverse events, adverse events of clinical interest (defined in Section 7.5), and events of overdose is available on the Serious Adverse Event report form and is as follows:

# For questions on Serious Adverse Event/Adverse Event of Clinical Interest reporting, please call:

- North/South America: PPD
- Europe, Asia, Pacific, and Africa: see region-specific phone numbers accompanying the Safety Reporting Form

The initial report should include:

- Study number (MVT-601-3102);
- Site address and number;
- Investigator name;
- Patient ID number, sex, and age;
- Details of study drug administration;
- The date of the report;
- A description of the serious adverse event (event term, seriousness of the event, date of onset, intensity);
- Causal relationship to the study drug.

If the patient died, the report should include the cause of death as the event term (with death as outcome) and whether or not the event leading to death was related to study drug treatment, as well as the autopsy findings if available.

Do not delay reporting a suspected serious adverse event in order to obtain additional information. Any additional information, if collected, can be reported as a follow-up to the initial report. All serious adverse events will be followed until resolution, until the event has stabilized, and/or reached a new baseline. All serious adverse events continuing at the completion of the study must be assessed or followed to determine outcome.

#### 7.7. Study Drug Overdose Management

The medical monitor must be contacted in the event of any study drug overdose.

An overdose is defined as a known deliberate or accidental administration of study drug, to or by a study patient, at a dose above that assigned to that individual patient according to the study protocol.

For this study, any dose of relugolix > 80 mg within a 24-hour window is an overdose and any dose of estradiol/norethindrone acetate > 2 x the protocol dose is an overdose (ie, more than 2 capsules taken within a 24-hour window). There is no known antidote for an overdose.

In the event of an overdose, the investigator or treating physician should:

- Contact the medical monitor immediately;
- Closely monitor the patient for adverse events and laboratory abnormalities;
- All overdose events are to be reported within 24 hours of awareness by the study site, using a serious adverse event form according to Section 7.6, whether or not the overdose is associated with an adverse event;
- Document the quantity of the excess dose as well as the duration of the overdosing in the eCRF.

The medical monitor, in consultation with the investigator, will make decisions regarding patient status and potential dose interruptions, based on the clinical evaluation of the patient.

#### 7.8. Pregnancy Reporting

If any patient becomes pregnant during the study, the site must discontinue the patient from the study treatment immediately and have her return for an Early Termination visit. The investigator must inform the patient of her right to receive treatment information. If the patient chooses to receive unblinded treatment information, the individual blind should be broken and the treatment assignment provided to the patient. The study team will remain blinded to the patient's treatment assignment.

If the patient agrees, the investigator should notify the patient's primary care physician of the pregnancy and provide details of the patient's participation in the study and treatment (blinded or unblinded, as applicable).

A pregnancy is to be reported to the sponsor within 24 hours of awareness by the study site personnel, using the Pregnancy reporting forms and contact information in Section 7.6. The expected date of delivery or expected date of the end of the pregnancy, last menstruation, estimated conception date, pregnancy result, and neonatal data, etc, should be included in this information, as available.

The investigator will follow the medical status of the mother, as well as the fetus, and will report the outcome to the sponsor.

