Run-In Day R1 is defined as the day that the first dose of single-blind study drug was taken. Once eligibility has been confirmed, patients will be randomized on Baseline Day 1 and will begin double-blinded study drug treatment on the same day. The Run-In Period through the day prior to the first dose of randomized study drug will serve as the Baseline pain assessment period for the study. During the Randomized Treatment Period, study participants will take the blinded study treatment (1 tablet and 1 capsule) orally once daily for 24 weeks. The last dose of study drug will be taken on the day prior to the Week 24 visit.

Between the Baseline Day 1 and Week 24 visits, patients will attend visits every 4 weeks. During the Run-In Period and at the Week 12 and Week 24 visits, each patient will have an assessment of bone mineral density with dual-energy x-ray absorptiometry (DXA). Patients will complete a daily eDiary from the day prior to Run-In Day 1 through the Follow-Up visit to record study drug treatment, assessment of pain using the NRS, menstrual bleeding and its severity, analgesic use, and the functional effects of endometriosis-associated pain (using Subject Modified Biberoglu and Behrman [sB&B]). Evaluation of function (using Endometriosis Health Profile [EHP] - 30), quality of life questionnaires, PGICs, and Patient Global Assessments (PGAs) for pain and a PGA for function will be completed as specified in the Schedule of Activities. Patients will continue use of protocol-specified rescue analgesic medications, as needed, until the end of the Follow-Up Period.

Safety will be assessed throughout the study by the monitoring of adverse events, vital signs and weight, physical examinations including visual acuity, clinical laboratory tests, 12-lead electrocardiograms (ECGs), and bone mineral density by DXA. Pharmacodynamics samples will be collected for assessment of luteinizing hormone (LH), follicle-stimulating hormone (FSH), estradiol, and progesterone at intervals during the study. Eligible patients, including women randomized to placebo, will be offered the opportunity to enroll in a 28-week open-label extension study where patients will receive relugolix co-administered with low-dose estradiol and norethindrone acetate. Patients who do not enroll into the extension study will have a Follow-Up visit approximately 30 days after the patient's last dose of study drug.

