- t. Procedure not required at the Early Termination visit in patients whose last dose of study drug was during Week 6 or earlier or within 4 weeks after completion of the Week 12 scan. The procedure may be done if it will aid in the evaluation of an ongoing adverse event.
- u. Schedule DXA as early as possible within the Week 24 visit window. Patients not proceeding to the extension study who have had a bone mineral density loss of > 2% at the lumbar spine (L1-L4) or total hip at their Week 24/Early Termination visit or most recent study scan relative to baseline (Run-In Period) will undergo another bone densitometry scan at 6 (± 1) months after the Week 24/Early Termination visit scan to evaluate recovery and will be contacted to question them about medications and conditions (eg, pregnancy) that might affect bone mineral density through the time of the repeat bone densitometry. The repeat bone densitometry will be submitted for central reading. It is recommended that this procedure be completed during Screening, whenever possible, rather than waiting until the Run-In Period.

Myovant Sciences GmbH 29 CONFIDENTIAL

v. Obtain sample with an endometrial suction curette (eg, Pipelle®). See the Laboratory Manual for guidance on handling and shipping the biopsy sample to the central laboratory for analysis. It is strongly recommended that this procedure be completed during Screening, rather than waiting until the Run-In Period. Patients who have a documented and adequate endometrial biopsy from within 6 months prior to Screening are not required to have another biopsy.

- w. Please see the Study Reference Manual for information on where and how to obtain protocol-specified analgesic medications by country. At the Week 24 visit, patients who will not be proceeding to the extension study will be re-dispensed or prescribed protocol-specified analgesic drugs, if needed, to ensure sufficient supply until the Follow-Up visit. For patients proceeding to the extension study, refer to the protocol for study MVT-601-3103.

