# 4.6. Removal of Patients from Therapy

Completion of the Week 24 visit defines completion of the study. Patients may withdraw consent to participate in the study and discontinue treatment at any time for any reason. Investigators or the medical monitor may remove patients from therapy under this protocol for reasons of safety and/or lack of compliance as discussed below. Patients removed from

randomized study treatment for any reason will undergo the assessments for the Early Termination visit (see Schedule of Activities, Section 1.1) and will have a Follow-Up visit to assess safety approximately 30 days after the end of study drug treatment (ie, after the patient's last dose of study drug). When patients complete the study or early terminate from the study, they must be deactivated from the study in the IVRS/IWRS, eDiary, and tablet device.

The following safety and/or compliance events will result in the removal of patients from therapy either permanently or until the etiology of the problem has been identified and resolved:

- Any adverse event that is intolerable to the patient and that cannot be ameliorated by the use of adequate medical intervention, or that in the opinion of the investigator or medical monitor would lead to undue risk to the patient if dosing continued;
- If it is discovered after randomization that a patient failed to meet protocol entry criteria and continued participation poses an unacceptable risk to the patient's health;
- If the following liver test abnormalities develop, study drug should be discontinued immediately with appropriate clinical follow-up (including repeat laboratory tests, until a patient's laboratory profile has returned to normal/baseline status):
  - $\circ$  ALT or AST > 8 x ULN; or
  - $\circ$  ALT or AST > 5 x ULN and persists for more than 2 weeks; or
  - o ALT or AST > 3 x ULN in conjunction with elevated total bilirubin > 2 x ULN or international normalized ratio (INR) > 1.5; or
  - o ALT or AST > 3 x ULN with appearance of fatigue, nausea, vomiting, right upper quadrant pain or tenderness, fever, rash and/or eosinophilia (> 5%);
- QTcF prolongation of more than 500 msec as read by a cardiologist;

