- Patients who are, in the opinion of the investigator or the medical monitor, grossly non-compliant with the protocol requirements. Gross noncompliance includes < 75% compliance with the study drug over > 2 consecutive months; missing multiple study visits; and persistent (> 2 consecutive months) with < 50% of the required number of days eDiary completion. Investigators will follow-up with the patient and encourage compliance with study drug or eDiary prior to discontinuing her from the study;
- Patients whose treatment assignment has been unblinded by the investigative site will be permanently discontinued from treatment;
- If the patient becomes pregnant at any time after providing a signed informed consent form, the patient must be withdrawn immediately (see Section 7.6 for information on pregnancy reporting);
- Should a patient fail to attend the clinic for a required study visit within the protocoldefined window, the site should attempt to contact the patient and reschedule the missed
  visit as soon as possible. Rescheduled visits conducted outside the visit window for the
  scheduled visit will be considered unscheduled. The site should also counsel the patient
  on the importance of maintaining the assigned visit schedule and determine whether the
  patient can and/or should continue in the study based on previous non-compliance. In
  cases where the patient does not return for the rescheduled visit or cannot be reached to
  reschedule the missed visit, the site should make every effort to regain contact with the
  patient. The site should attempt at least 3 documented telephone calls and if necessary a

certified letter to the patient's last known mailing address so that they can appropriately be withdrawn from the study with a primary reason of "Lost to follow-up."

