#### 6.7. Early Termination Visit and Follow-Up Visit

Refer to the Schedule of Activities (see Section 1.1) for individual study visit procedures during the Early Termination visit and Follow-Up visit.

All patients withdrawing from the study prior to Week 24 will complete an Early Termination visit. The Early Termination visit procedures are identical to those of Week 24; however, for patients whose last dose of study drug is during Week 6 or earlier, the endometrial biopsy does not need to be performed. This procedure may be performed, however, at the investigator's discretion, if it aids in follow-up of an ongoing adverse event. The DXA is not required at the Early Termination visit in patients whose last dose of study drug was during Week 6 or earlier or within 4 weeks after completion of the Week 12 scan.

All patients who do not wish to or who are not eligible to enroll in the extension study (MVT-601-3103), will have a Follow-Up visit approximately 30 days after the last dose of study drug, or prior to the date of initiation of another investigational agent or hormonal therapy affecting the hypothalamic-pituitary-gonadal axis or surgical intervention for endometriosis, whichever occurs first. This visit will be used to assess safety after discontinuation of study treatment including adverse events, clinical safety laboratories, 12-lead ECG, and return of menstruation.

Patients who withdraw early from this study will undergo the Follow-Up visit approximately 30 days after the last dose of study drug, or the date of initiation of another investigational agent or hormonal therapy affecting the hypothalamic-pituitary-gonadal axis or surgical intervention for endometriosis, whichever occurs first.

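### The Early Termination visit after withdrawal for pregnancy includes DXA, and neither that scan nor the 6-month repeat scan has a pregnancy exception

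*Protocol*

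**What the plan says.** On pregnancy, Section 7.8 states that "the site must discontinue the patient from the study treatment immediately and have her return for an Early Termination visit". Section 4.6 agrees: "If the patient becomes pregnant at any time after providing a signed informed consent form, the patient must be withdrawn immediately". Its general rule is that patients removed from "randomized study treatment for any reason will undergo the assessments for the Early Termination visit".

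Section 6.7 defines the content of that visit: "The Early Termination visit procedures are identical to those of Week 24". Section 6.5 and the Schedule of Activities (Section 1.1) both place bone densitometry at Week 24, and the Schedule marks it in the combined Week 24/Early Termination column.

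Section 6.7 then gives the exceptions: "The DXA is not required at the Early Termination visit in patients whose last dose of study drug was during Week 6 or earlier", or when the last dose fell within 4 weeks after the Week 12 scan. Footnote t of the Schedule repeats both: "Procedure not required at the Early Termination visit in patients whose last dose of study drug was during Week 6 or earlier", plus the same 4-week clause. Neither place mentions pregnancy.

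For women who do not enter the extension and have lost more than 2% at the lumbar spine or total hip, footnote u says they "will undergo another bone densitometry scan at 6 (± 1) months after the Week 24/Early Termination visit scan to evaluate recovery". Section 6.8 has the same requirement, counted from stopping study drug. In both places the site must ask about pregnancy, but only as something that may influence bone density.

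**The concern.** The protocol withdraws a woman because she is pregnant and sends her to a visit whose procedure list includes an x-ray-based scan. It considers when that scan should be omitted and lists the cases, and pregnancy is not among them. The list appears twice, so the gap is not a slip in one place.

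At stake is an avoidable x-ray procedure in a known pregnancy. The scan would also be of little use, since the protocol itself treats pregnancy as a condition that may affect bone density. A site that sensibly leaves the scan out is exposed as well: Section 10.1.9 requires conduct according to the protocol, and Section 10.2.2 bars deviation without prior sponsor approval (and ethics committee approval where required) except in medical emergencies. A positive urine test at a routine visit is not obviously an emergency.

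**Working it through.** The plan states no figure on this point. The check is whether a scheduled pregnancy test can turn positive when neither waiver applies.

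**Inputs.** Nominal visit days and windows come from the Schedule of Activities: Week 4 = Day 29, Week 8 = Day 57, Week 12 = Day 85, Week 16 = Day 113, Week 20 = Day 141, each ± 7 days, with a urine pregnancy test at each. Assumptions: she doses up to the visit, so her last dose is the visit day; Week 6 ends on Day 6 × 7 = 42; the Week 12 scan is on Day 85, so the second waiver ends on Day 85 + 28 = 113.

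| Positive test at | Last dose | Week 6 waiver (to Day 42) | Post-scan waiver (Days 85–113) | DXA called for |
|---|---|---|---|---|
| Week 4 | Day 29 | applies | – | no |
| Week 8 | Day 57 | no, 57 > 42 | no, 57 < 85 | yes |
| Week 12 | Day 85 | no | only if the scan came first | depends on order |
| Week 16 | Day 113 | no | applies, on its last day | no |
| Week 20 | Day 141 | no | no, 141 > 113 | yes |

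**Visit windows.** The earliest Week 8 visit is Day 57 − 7 = 50, still after Day 42. The latest is Day 64, before the earliest Week 12 scan on Day 78. The earliest Week 20 visit is Day 134, and the latest end of the second waiver is Day 92 + 28 = 120. Weeks 8 and 20 therefore stay uncovered wherever the visits fall in their windows. Taking the last dose as the day before the visit (Days 49 and 133 at the earliest) changes nothing. Week 16 is less secure: with the scan on Day 78 the waiver ends on Day 106, before a visit on Day 113.

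**Earlier stopping.** The waiver depends on last dose, so a woman who had already stopped could qualify. On nominal days that needs 57 − 42 = 15 days off drug before a Week 8 test, or 141 − 113 = 28 days before a Week 20 test.

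**Repeat scan.** A woman withdrawn for pregnancy before Week 24 does not enter the extension, which Section 5.10 describes for those completing 24 weeks. The 2% rule can be triggered by her most recent study scan, so a Week 12 scan is enough even if no Early Termination scan is taken. Assume the pregnancy was found at 4 to 8 weeks' gestation. Six ± 1 months is about 22 to 30 weeks, so the repeat scan falls at 22 + 4 = 26 to 30 + 8 = 38 weeks. A continuing pregnancy would then usually still be in progress, taking term as 40 weeks. A new pregnancy is also possible: Section 4.7 requires contraception for 30 days after the last dose, which leaves about 5 − 1 = 4 to 7 − 1 = 6 months before the scan.

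**The case against.** The strongest reply is that the protocol is only one of the governing documents. Section 6 leaves further procedural detail to the Study Reference Manual. Section 6.10.2.8 leaves detailed DXA instructions to the same manual and also cites an imaging charter and a central radiology charter. None is shown, and any of them may exclude pregnant women. Pregnancies reach the sponsor within 24 hours of site awareness (Section 7.8), scans are done at facilities trained by the central radiology vendor (Section 6.2), and Section 10.1.1 holds investigators to whichever standard better protects the participant. So a reader might infer that sites would in fact scan pregnant women. The documents do not support that; they support only that the written rule calls for it. Still, Section 6.7 and footnote t do not refer to another document for exemptions.

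For the repeat scan, the required contact about pregnancy and the as-needed urine test at unscheduled visits (Section 6.9) give the site a way to learn of a pregnancy. That stands, but nothing says what to do on learning of it. Ending required contraception 30 days after the last dose is not itself a fault.

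Three stronger readings should be resisted:

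- The share of treatment days outside the waivers is not a measure of risk. It treats every last-dose day as equally likely, whereas scheduled testing is monthly and the timing of pregnancies is unknown.
- The gap does not contradict Table 7-2. Its reproductive toxicity row concerns relugolix, lists contraception, exclusion and monthly testing as well as withdrawal, and does not deal with imaging.
- No fetal dose or harm can be claimed, because the documents quantify neither.

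**Conclusion.** The point holds as a gap in the protocol's wording. Followed exactly, the text calls for a DXA scan in a woman just withdrawn for pregnancy unless one of two timing conditions happens to apply. On the schedule, a positive test at Week 8 or Week 20 in a woman still dosing meets neither. The repeat scan has the same gap, limited to women outside the extension with more than 2% loss.

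The size is small. Nonhormonal contraception is required unless an exemption applies, so few women would be affected, and the number cannot be estimated from the protocol. Sample size and the primary analysis are untouched, and the bone density analyses are essentially unchanged. Confidence is high about the wording and does not extend to how often it would matter or to what the unseen manual and charters say. It should be corrected because it is a patient safety rule that costs almost nothing to put right.

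**What to change.** In Section 6.7 and footnote t, add a third exception: *DXA is not performed at the Early Termination visit in a patient who is pregnant.* Cross-refer to it from Section 7.8.

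In Section 6.8 and footnote u, add: *The repeat scan is not performed while the patient is pregnant; whether to scan after the pregnancy ends is decided with the medical monitor.* An automatic deferral to the end of pregnancy would be less sound, because the scan is meant to show recovery at about 6 months, and a late scan after pregnancy may not show it.

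If the manual or charters already contain such a rule, the protocol text should be brought into line with it. The cost is a few clauses in one amendment and a few missing scans. Any scan taken after a pregnancy will be harder to read as recovery from study drug.
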